#### 7.2.1.5 Intercurrent events

Use of open label corticosteroids (i.e., discontinuation of study IMP during D1-D6 and initiation of corticosteroids due to deterioration of the study subjects' condition, or initiation of corticosteroids D7 onwards) is an intercurrent event anticipated to affect the study outcomes. The primary analysis is planned to follow the treatment policy strategy (using FAS dataset). As sensitivity analyses, also other strategies under the estimands framework (ICH E9 (R1) addendum) will be applied to account

for this intercurrent event. Details of these analyses will be described in SAP. The frequency and magnitude of the effect of the use of corticosteroids to the study outcomes will be also evaluated during the planned Interim Analysis.

### 7.3 Demographics, Medical History, Baseline Characteristics and Concomitant Medications

Baseline assessments will consist of those assessments carried out in the screening period and those carried out prior to the first dose of study drug on D1.

Demographic and baseline characteristics will be summarised by treatment group and overall. No formal statistical comparisons will be undertaken to compare treatment groups for any of these parameters.

Demographic data, medical history, concomitant disease and concomitant medication will be summarised by descriptive statistics (number, mean, SD, median, minimum and maximum) or frequency tables, overall and stratified by treatment.

A medication given prior to the first injection of study drug will be classified as a prior medication. A medication given with or after the first injection of study drug will be classified as concomitant. Prior medications continuing during the study will be labelled accordingly in the listings.

### 7.4 Determination of Sample Size

140 patients will be randomised 1:1 for active: comparator. Conditional Power re-assessment will be conducted at interim analysis after circa 70 patients have been enrolled and followed up for the primary efficacy endpoint variable. The primary variable is the clinical status at Day 14 using the WHO 9-point scale (0=no detectable infection to 8=death). It will be analysed using ordinal logistic regression model comparing the odds of having better clinical status (smaller number in the 9-point scale) at Day 14 between treatment groups. The sample size is based on an assumption of odds ratio of 0.43 between groups leading to a power of 80% with 70 evaluable patients per group. In the interim analysis the conditional power will be calculated based on the observed result and the sample size will be increased in case the conditional power is in the predefined promising zone. The details of interim analyses will be given in IDMC charter created at the study initiation and in an interim analysis plan which will be finalised before breaking the blind for interim analysis.

### 7.5 Efficacy Analyses

#### 7.5.1 Primary Efficacy Analysis

For the Primary Efficacy Endpoint the following hypotheses will be tested:

- Null hypothesis  $H_0$ : the WHO OSCI at D14 in the IFN beta-1a treatment group is equal to that in the control group
- Alternative hypothesis  $H_A$ : the WHO OSCI at D14 in the IFN beta-1a treatment group is not equal to that in the control group

The primary analysis of this endpoint will be based on the FAS, with a sensitivity analysis based on the PPS providing supportive information. Each of these analyses will be undertaken at the two-sided significance level of 0.05. For powering of the primary efficacy endpoint see chapter 7.4.

The primary variable will be analysed using ordinal logistic regression model comparing the odds of having better clinical status (smaller number in the scale from 0 to 8) between the groups. The primary model will include baseline OSCI score and age, gender and ethnicity as a covariate. In

addition, also a model without covariates will be applied and the results provided as sensitivity analysis. The percentages in each category for both groups will be presented descriptively including 95% confidence intervals.

Primary endpoint as well as other efficacy endpoints will also be presented for key predefined subgroups of patients (such as SNP rs9984273, see [Section 4.2.3](#)) together with 95% CIs for the difference in those rates to supplement the investigation of homogeneity.

### **7.5.2 Secondary Efficacy Analyses**

For the Secondary Efficacy Endpoint WHO OSCI score at Day 28 will be analysed in a similar ordinal logistic regression model than the primary endpoint.

The primary analysis of the mortality endpoints (in-hospital and overall (all-cause) mortality at Days 28 and 90) will be based on the FAS and will be undertaken using COX proportional hazards regression model adjusting for age, gender and ethnicity key baseline characteristics. This analysis will be repeated using the PPS as a sensitivity analysis. Hazard ratios comparing the treatment groups will be reported using 95% CI for these endpoints. Data for these efficacy endpoints will also be presented for key predefined subgroups of patients (such as SNP rs9984273, see [Section 4.2.3](#)) together with 95% CIs for the difference in those rates to supplement the investigation of homogeneity.

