Study subjects will be randomized in a 1:1 ratio of IFN beta-1a: dexamethasone. According to current NIH COVID-19 treatment guidelines, dexamethasone can be considered for all patients receiving increasing amounts of supplemental oxygen, but remdesivir without dexamethasone is a reasonable

treatment option for patients requiring minimal levels of supplemental oxygen. Remdesivir does not impact study treatment.

In the current study, the target population is mild COVID-19 subjects with a need for low levels of supplemental oxygen. Subjects randomised to IFN beta-1a treatment will not receive dexamethasone while on IFN beta-1a, but will receive it if deterioration occurs, at which point IFN beta-1a will be discontinued. However, not receiving dexamethasone should not subject the study participants to an increased risk for harm for the following reasons:

In the RECOVERY trial (on which the NIH recommendations are largely based), increasing benefit from corticosteroids was associated with increased COVID-19 severity. The greatest benefit was seen in patients receiving invasive mechanical ventilation, somewhat less benefit in patients receiving supplemental oxygen (but not invasively ventilated), and no benefit – with a suggestion of harm - in patients not receiving supplemental oxygen (The RECOVERY Collaborative Group 2020). Unfortunately, the RECOVERY trial data were not sufficiently granular to identify the impact of the dose of oxygen in non-intubated patients, i.e., supplemental oxygen at low flows vs higher flow conventional oxygen vs high flow nasal oxygen vs non-invasive ventilation. Nonetheless, these data suggest a dose-response curve for benefit in relation to the patient's underlying severity of disease, as determined by the application of supplemental oxygen. Given this dose-response, it is uncertain if subjects with low flow supplemental oxygen derive any benefit from dexamethasone.

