#### Secondary Efficacy Endpoints:

- Clinical status at D28 as measured by WHO 9-point ordinal scale (above)
- Secondary endpoints relating to the efficacy of IV IFN beta-1a treatment:
  - In-hospital mortality at Day 28 and Day 90
  - Overall (all-cause) mortality at Day 28 and Day 90

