## 7.2 General Considerations

All statistical tests will be two sided and will be performed at the significance level of 0.05, unless otherwise stated.

Continuous data will be summarised by treatment group using descriptive statistics (number, mean, median, standard deviation [SD], minimum and maximum). Categorical data will be summarised by treatment group using frequency tables (frequencies and percentages).

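### The Cox models for mortality have no sparse-event fallback and no overall risk difference; at about 5% mortality or below the hazard ratio may have no finite estimate

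*Protocol*

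**What the plan says.** Protocol 4.2.2 lists four mortality endpoints among the secondary efficacy endpoints: "In-hospital mortality at Day 28 and Day 90" and "Overall (all-cause) mortality at Day 28 and Day 90". Section 7.5.2 says that their main analysis, on the full analysis set, is a Cox model "adjusting for age, gender and ethnicity key baseline characteristics". The analysis is repeated on the per-protocol set. The overall treatment comparison is a hazard ratio with a 95% CI. The same paragraph adds subgroup presentations with CIs for rate differences.

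On size, section 7.4 states that "140 patients will be randomised 1:1 for active: comparator". On severity, section 2.6 says that "the target population is mild COVID-19 subjects with a need for low levels of supplemental oxygen". The protocol gives no expected death rate, no minimum number of deaths for fitting the model, no number of ethnicity levels and no alternative if deaths are too few.

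The plan does provide alternatives elsewhere. Section 7.5.1 adds a model without covariates for the primary endpoint, and section 7.5.3 allows a Wilcoxon test for the days-free endpoints if no distributional assumption is valid. Mortality has neither kind of provision.

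**The concern.** With treatment, age, gender and ethnicity, the model has at least four parameters, and more if ethnicity has over two levels. If a mild population produces only a handful of deaths, two problems arise.

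- If one arm has no deaths, the maximum-likelihood log hazard ratio runs to plus or minus infinity, and the planned estimate and interval cannot be reported in a usable form.
- If both arms have deaths but few, the estimate exists but is very imprecise, and every extra covariate spends events that the treatment comparison needs.

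Mortality should be readable in either direction here. Section 2.6 explains that patients on IFN beta-1a do not receive dexamethasone unless they deteriorate. Section 2.3.3 reports Day 28 mortality of 40% on IFN beta-1a against 21% on placebo in the Japanese phase III trial, although that was a different population. A split such as several deaths against none is where a reader most needs a usable number, and it is where the planned estimate fails.

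**Working it through.** **The plan's own figure.** The only power statement is for the primary ordinal endpoint: "an assumption of odds ratio of 0.43 between groups leading to a power of 80% with 70 evaluable patients per group". The Whitehead proportional-odds formula is N = 12(z_a + z_b)² / [ln(OR)² × (1 − Σp̄³)]. With two-sided 0.05 and 80% power the leading term is 12 × (1.960 + 0.842)² / ln(0.43)² = 132.2. With 4 to 9 equally filled categories N is 141 down to 134, so 140 is plausible. The category distribution is not in the documents, so this is a conditional check only (with 60% of controls in one category, N would be about 198). It says nothing about mortality.

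**Inputs.** 70 patients per arm (7.4); two-sided 0.05 (7.2); at least four model parameters (7.5.2). *Assumption:* mortality m of 2% to 20%, equal in both arms unless stated.

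**Formulas.**
- Expected deaths: d = 140m.
- Chance that at least one arm has no deaths: 1 − [1 − (1 − m)^70]².
- Approximate 95% CI factor each way around the hazard ratio: exp(1.96 × √(4/d)).
- Events per parameter: d/4.

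| Assumed mortality | Deaths | At least one arm with none | CI factor | Deaths per parameter |
|---|---|---|---|---|
| 2% | 2.8 | 43% | 10-fold | 0.7 |
| 3% | 4.2 | 22% | 6.8-fold | 1.05 |
| 5% | 7 | 5.4% | 4.4-fold | 1.75 |
| 10% | 14 | 0.1% | 2.9-fold | 3.5 |
| 20% | 28 | about 0% | 2.1-fold | 7.0 |

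Worked line for 5%: 0.95^70 = 0.0276, so 1 − (1 − 0.0276)² = 0.054; and exp(1.96 × √(4/7)) = 4.4, so an observed hazard ratio of 1 would have an interval of about 0.23 to 4.4.

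If mortality were 5% on dexamethasone and 2.5% on IFN beta-1a: 0.975^70 = 0.170, so 1 − (1 − 0.0276)(1 − 0.170) = 0.193.

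**High-end stress test.** The INTEREST rates in section 2.3.3 (26% and 23%, in ARDS) would give 70 × 0.26 + 70 × 0.23 = 34.3 deaths, or 8.6 per parameter, and a CI factor of about 1.95.

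**Covariates.** Simulating 400 trials at 5% mortality under no effect, with a two-level ethnicity variable, gave no usable treatment hazard ratio in about 8%. Some treatment, gender or ethnicity level had no deaths in about 25%. With four ethnicity levels, some level had no deaths in about 79%. The age effect, ethnicity shares and constant hazard are assumptions, so the binomial figures are the firmer evidence.

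**Limit of any remedy.** Power to detect a hazard ratio of 0.5 is about 15% at 5% mortality and 25% at 10%. Detecting it with 80% power needs about 66 deaths: 4 × (1.960 + 0.842)² / ln(0.5)² = 65.3. Penalisation gives a finite, interpretable estimate; it does not add information.

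**The case against.** **No death rate supports the premise.** This is correct. Mild is the sponsor's label for hospitalised adults on oxygen, with no upper age limit and a stratum aged 70 and over (4.5, 4.10.2). At 10% mortality the zero-death problem nearly vanishes. The interim analysis may also increase N, though the protocol states no maximum. A reader might infer that the hazard ratio is bound to fail; the documents do not support that.

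**Absolute mortality is not ignored.** A reader might infer that the plan offers nothing but hazard ratios. It offers more. Section 7.2 summarises categorical data by arm as counts and percentages. Section 7.5.1 gives percentages with 95% CIs for each category of the WHO scale, which includes death, and Day 28 is analysed similarly. Section 4.2.1 makes deaths to Day 90 a safety criterion, and section 7.6.1 lists adverse events leading to death. Section 7.5.2 has subgroup rate differences. What is missing is the overall between-arm risk difference with an interval. The Synopsis names logistic regression for dichotomous secondary variables, but without penalisation that fails in the same way when one arm has no deaths.

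**The test would be far too conservative.** A reader might also infer this. In 600 simulated null trials per rate, with four ethnicity levels assumed, a Wald test rejected in 0.3%, 1.5% and 4.0% at 3%, 5% and 10% mortality. But the protocol specifies no Wald test, the four levels are an assumption, and Fisher's exact test behaves much the same (0.5%, 1.4%, 2.5%). Few events are a large part of the cause. A score test stays closer to nominal (4.1%, 4.8%, 5.1%), which argues for a score-type interval over an exact one.

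**Importance.** Mortality is an unpowered secondary endpoint in a phase II trial, and Day 28 clinical status, which includes death, is listed first. The Japanese figures come from ARDS patients with 77% corticosteroid use. Neither supports calling mortality the decisive evidence or treating those figures as a forecast here.

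**Conclusion.** The point holds as a cheap improvement to the protocol's planned analysis. If mortality is about 5% or below, the stated method has a material chance of giving no finite hazard ratio: 5% of trials at 5% mortality, 22% at 3%, and 19% at 5% versus 2.5%. At 10% the hazard ratio is normally estimable, but with an interval of roughly 3-fold each way. These sizes rest on assumed mortality rates and on 70 patients per arm. In-hospital deaths cannot exceed all-cause deaths, so the in-hospital endpoints are at least as exposed.

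A reader might infer that the trial's reported findings are affected. They are not. SAP sections 2 and 6 record termination after five patients, set no formal hypotheses and present the data descriptively, with deaths listed. No Cox model remains. The point matters for the protocol as designed and for any later trial that reuses it.

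**What to change.** In Protocol 7.5.2:

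- Report the number of deaths by arm and the overall Day 28 and Day 90 risk differences, each with a score-type 95% CI, for both in-hospital and all-cause mortality.
- Fit the Cox model with Firth penalisation and report profile-likelihood 95% CIs.
- Adjust for age and gender, which are the randomisation stratification factors (4.10.2), and omit ethnicity. This leaves three parameters if age is a single term: at 5% mortality, 7/3 = 2.3 deaths per parameter instead of at most 1.75.

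The cost is a few sentences and one software option. The risk difference needs vital and hospital status at Days 28 and 90, which sections 6.3.3 and 6.4 already collect. The statistical price is slight shrinkage of the hazard ratio and no ethnicity adjustment for mortality. The intervals will still be wide, and the text should not suggest otherwise. The SAP needs no change, since it no longer contains this analysis.

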### **7.5.3 Exploratory Efficacy Endpoints**

#### **Incidence of ARDS and AKI**

The binary variables for incidence of mechanical ventilation, ARDS and AKI (until Day 28) will be analysed with logistic regression model with similar covariates than used for the primary endpoint analysis. Odds ratios comparing the treatment groups will be reported using 95% CI for these endpoints.

#### **Days Free of Renal Support, ECMO, Oxygen support, Mechanical ventilation, ICU and Hospital Care**

Renal support -free days alive are defined as the number of days in the first 28 days after the first dose of study drug that the patient is alive and free of renal support (renal replacement therapy).

In similar fashion days alive and free from mechanical ventilation, ECMO, oxygen support, length of hospital and of ICU stay at D28 will be evaluated.

General linear mixed model will be used for the analysis of these endpoints. However, if there is no valid distribution assumption, then Wilcoxon rank sum test will be applied. The statistical methods to be used for these exploratory efficacy endpoints will be detailed further in the SAP.

#### **Incidence of study treatment discontinuation and transition to an open label corticosteroid**

The frequency and the onset date of the use of open label corticosteroids between the groups will be analyzed with general linear mixed model. However, if there is no valid distribution assumption, then Wilcoxon rank sum test will be applied. The statistical methods to be used for these exploratory efficacy endpoints will be detailed further in the SAP.

#### **Laboratory variables**

Descriptive statistics (mean, median, SD, minimum and maximum) for laboratory variables will be obtained and tabulated by treatment group. The statistical methods to be used for the analysis of laboratory exploratory endpoints will be detailed in the SAP.

## SARS-CoV-2 variant and SARS-CoV-2 vaccination status

Effect of SARS-CoV-2 variant and SARS-CoV-2 vaccination status on the primary and secondary efficacy endpoints will be explored using these variables as subgroups and presenting the results for each subgroup with 95% confidence intervals.

## 7.6 Safety Analyses

These summaries will be based on the safety set. The presence of anti-drug antibodies to IFN beta-1a at D28 will be summarised by treatment groups in terms of counts.

### 7.6.1 Adverse Events

AEs and SAEs will be coded using the current version of Medical Dictionary for Regulatory Activities (MedDRA) and will be classified by system organ classes and preferred terms. In the event that intensity or relationship of an AE to the study drug is missing, a worst-case scenario will prevail (severe in intensity or probably related). Only TEAEs (AEs that occur after the first study drug administration, that were not pre-existing or that increased in intensity) will be included in the summary tables. Counting will be performed for patients and events separately. Patients experiencing the same event more than once will have that event counted once within the corresponding system organ class and with a unique preferred term. All AEs will be included in the data listings. Listings of SAEs, of AEs leading to study drug withdrawal and of AEs leading to death will also be provided.

